1.2.2. Scientific Rationale for Study Design

The study design involves a 3+3 approach (commonly used in conducting phase 1 oncology studies) that allows the assessment of DLTs but does not include a dose escalation or de-escalation component. It is a well-established design for selecting a dose suitable for further investigation whilst minimising unnecessary exposure. In this study the design is employed to confirm the safety and tolerability of encorafenib 300 mg QD monotherapy in Chinese participants with *BRAF* V600E mutant melanoma or NSCLC to support further clinical development in combination with binimetinib.

1.2.3. Justification for Dose

The dose of encorafenib is 300 mg per oral (PO) QD, corresponding to its single agent Recommended Phase 2 Dose (RP2D). This dose has also been shown in clinical studies to result in tumor regression and clinical responses as a single agent (see Protocol Section 2.1.4).

1.2.4. End Of Study Definition

The end of study is defined as the timepoint when the last participant enrolled has discontinued study treatment and completed the 30-day safety follow-up.

2. Statistical Hypotheses

Because of the exploratory nature of the study, all data will be analyzed descriptively and not with an inferential approach. No formal statistical testing will therefore be performed.

2.1. Adjustment for multiplicity

Not Applicable.

3. Sample Size Determination

The planned sample size is up to six evaluable participants based on an approach that is similar to a 3+3 design (see Section 1.2). No formal sample size calculation has therefore been performed and sample size is based upon empirical considerations.

Participants will receive encorafenib 300 mg QD. This dose will be considered acceptable if the observed Cycle 1 DLT rate in evaluable participants is <33% (e.g. less than one participant with DLTs out of three participants or less than two participants with DLTs out of six participants). To be evaluable, participants must have *either* experienced an event meeting the DLT criteria in Cycle 1 *or* completed at least one cycle of study treatment and received at least 75% of the encorafenib dose intensity (administered dose in mg/planned dose in mg) in Cycle 1 (see Section 1.2).

4. Analysis Sets

The following populations will be analyzed:

4.1. Safety Set (SAF)

All participants who receive at least one dose of encorafenib (partial or full).

4.2. Dose-Determining Set (DDS)

All evaluable participants from the SAF who either achieve the minimum exposure requirement* and have sufficient safety evaluations** or experience a DLT.

*Encorafenib dose intensity of 75% (administered dose in mg/planned dose in mg) in Cycle 1

**Participants must have been observed for at least 1 cycle: (≥ 28 days) following the first dose on Cycle 1 Day 1.

4.3. PK Set

All participants who receive at least one dose of encorafenib and who have at least one postdose PK blood collection with associated bioanalytical results.

5. Statistical Analyses

5.1. General Considerations

All analyses will be performed using the SAF otherwise specified. Individual data will be listed on specific population as specified in the list of TFLs. In SAF and PK listings, participants excluded from DDS will be flagged (*).

Statistical analysis will be performed after database lock or data snapshot (see Protocol Section 10.1.8.3.5), using statistical analysis software (SAS[®]) Version 9.4 or higher.

In general, following descriptive methods will be used to present all relevant data:

- Continuous data will be presented using number of observations, number of missing (if any), mean, standard deviations, median, Q1, Q3, minimum and maximum. 95% Confidence Intervals (CI) will be presented if relevant.
- Categorical data will be summarized using number of observations, frequencies, percentages and number of missing (if any missing). Unless otherwise specified, the calculation of proportions will be based on the non-missing data. Counts of missing observations will be excluded from the denominator.

Baseline is defined as the last completed and available assessment prior to date of first dose of study treatment (including unscheduled or re-test). If an assessment that is planned to be performed prior to the first dose of study treatment in the protocol is performed on the same day as the first dose of treatment and the time is unknown, it will be assumed that it was performed prior to study treatment administration and will be considered as baseline assessment.

Unscheduled assessments will be used in the determination of baseline. Data reported at the end of treatment visit are not eligible for baseline selection.

ECG Baseline will be the mean of the last triplicate measurements performed before the first study treatment administration (i.e. screening assessment per Table 3 Schedule of Activities). If no triplicate available, then baseline will be the last single ECG measurement performed before the first study treatment administration. For the interpretation parameter (normal/abnormal and its related clinical significance), the baseline will be the last completed and available assessment performed before the first study treatment administration, regardless triplicate or single ECG.

For summary statistics by visit, only scheduled visits will be summarized. Re-test and unscheduled assessments will not be taken into account for summaries of post-baseline visit. For analyses of worst post-baseline assessment, all on-treatment values are considered regardless scheduled or unscheduled. For visits where triplicate ECG are collected, value of numeric parameters will be the average, and value of interpretation will be last non-missing record (ie both interpretation and clinical significance if abnormal should be non-missing).

For TFLs, visits will be identified as collected in CRF.

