8.3.6. Vital Signs

Tympanic temperature, pulse rate, respiratory rate, systolic blood pressure and diastolic blood pressure will be measured using study site standard techniques at screening and repeated on Cycle 1 Days 1, 8, 15 and 22, Day 1 of each subsequent cycle, the end of treatment visit and the 30-day safety follow-up visit. Blood pressure and pulse measurements should be preceded by at least 5 minutes of rest for the participant in a quiet setting without distractions (e.g. television, cell phones). All assessments during the treatment phase should be made prior to study treatment administration and before blood collection for laboratory tests.

Any treatment-emergent abnormal findings should be recorded as adverse events.

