9.4. Statistical Analyses

9.4.1. General Considerations

All data will be listed. This section summarizes the descriptive analyses planned on these data.

A SAP will be prepared by the sponsor (or designee) and finalized prior to first participant first visit. This plan will include a more technical and detailed description of the statistical analyses described in this section. This section is a summary of the planned statistical analyses. Any major modifications will also be described in a protocol amendment.

Statistical analysis will be performed after database lock or data snapshot (see Section 10.1.8.3.5), using statistical analysis software (SAS[®]) Version 9.4 or higher, according to the SAP.

In general, following descriptive methods will be used to present all relevant data:

- Continuous data will be presented using number of observations, number of missing, mean, standard deviations, median, quartiles, minimum and maximum. 95% CIs will be presented if relevant.
- Categorical data will be summarized using number of observations, frequencies, percentages and number of missing. Unless otherwise specified, the calculation of proportions will be based on the non-missing data. Counts of missing observations will be excluded from the denominator if not otherwise specified in the SAP.

Baseline is defined as the last completed and available assessment prior to date of first dose of study treatment. If an assessment that is planned to be performed prior to the first dose of study treatment in the protocol is performed on the same day as the first dose of treatment and the time is unknown, it will be assumed that it was performed prior to study treatment administration and will be considered as baseline assessment.

The Clinical Study Report will be written based on all data at the end of the study.

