1.2.1. Study Procedures and Assessments

For each participant, the study will include:

1. **Screening:** Participants with a locally determined *BRAF* V600E mutation will provide informed consent for screening and study procedures and assessments and will be screened for eligibility in the 28 days before the first dose of encorafenib.
2. **Treatment Period:** Participants fulfilling all the eligibility criteria (see Protocol Section 5) will receive encorafenib 300 mg QD in 28 day (\pm 7 days) cycles until death, disease progression (in special circumstances, continuation of treatment beyond disease progression may be allowed (see Protocol Section 6.1)) or one of the other predefined criteria for study treatment discontinuation is met (see Protocol Section 7.1). The participants will be evaluated for DLTs during the first cycle of treatment (28 days) [the DLT evaluation period]. An end of treatment visit will be completed at the time of study treatment discontinuation (as soon as possible and \leq 14 days after the last dose of study treatment).
3. **A 30-day Safety Follow-up:** A safety follow-up visit will be performed approximately 30 days after the last dose of study treatment or before the initiation of subsequent anticancer therapy, whichever occurs first.

The schedule of activities for each participant is shown in Table 3.

Table 3: Schedule of Activities

Cycle / Visit	Screening	Cycle 1			Cycle 2		Subsequent Cycles[a]			EOT visit	Safety 30-day follow-up visit[b]	
		D1[c]	Inclusion/ Baseline	D8	D15	D22	D1 ± 3 days	D28 ± 7 days	D1 ± 3 days	D28 ± 7 days		
Day -28 to -1												+ 7 days after EOT visit/last dose if EOT not performed
EPOCH	SCREENING	SCREENING	TREATMENT									FOLLOW -UP
Main study informed consent	X											
Inclusion/exclusion criteria	X	X										
Demographic data	X											
Medical and disease history	X											
Prior medications/therapies/procedures	X											
Smoking habits	X											
ECOG performance status	X	X					X		X	X	X	X
Height	X											
Physical examination[d] and body weight	X	X[h]	X	X	X	X		X	X		X	X
Vital signs[e]	X	X	X	X	X	X		X	X		X	X
Dermatological examination[f]	X							X			X	X
Hematology[g]	X	X[h]		X		X		X	X		X	X

Cycle / Visit	Screening	Cycle 1			Cycle 2		Subsequent Cycles[a]			EOT visit	Safety 30-day follow-up visit[b]	
							Odd cycles	Even cycles				

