Day -28 to -1	D1[c] Inclusion/ Baseline	D8	D15	D22	D1 ± 3 days	D28 ± 7 days	D1 ± 3 days	D1 ± 3 days	D28 ± 7 days	± 3 days	+ 7 days after EOT visit/last dose if EOT not performed	
Clinical chemistry[i]	X	X[h]		X		X		X	X		X	X
Coagulation[j]	X	X[h]		X		X		X	X		X	X
Urinalysis tests[k]	X	X[h]	X	X	X		X	X			X	X
Hepatitis B, C markers and HIV[l]	X											
Pregnancy test[m]	X	X[h]				X		X	X		X	
Chest, abdomen and pelvis CT scan[n]	X						X			X	X	X
MRI or CT scan of brain with IV contrast (if clinically indicated)[n]	X						X			X	X	X
Bone scan or PET scan (if clinically indicated)	X						X			X	X	X
12-lead ECG[o]	X		X	X	X			X			X	
Encorafenib dispensation (plus dosing diary)		X				X		X	X			
Encorafenib compliance assessment						X		X	X		X	
Concomitant medications/therapies	Assess continuously											
AE assessment (NCI CTCAE Version 4.03)	Assess continuously											
PK blood samples[p]		X				X						

Cycle / Visit	Screening	Cycle 1			Cycle 2		Subsequent Cycles[a]			EOT visit	Safety 30-day follow-up visit[b]
		D1[c]	Inclusion/ Baseline	D8	D15	D22	D1 ± 3 days	D28 ± 7 days	D1 ± 3 days		
Day -28 to -1											+ 7 days after EOT visit/last dose if EOT not performed
Abbreviations: AE = adverse event; ALT = alanine aminotransferase; aPTT = activated partial thromboplastin time; AST = aspartate aminotransferase; β-HCG = beta human chorionic gonadotropin; BUN = blood urea nitrogen; CK = creatine kinase; CT = computed tomography; eCRF = electronic case report form; D=Day; ECG = electrocardiogram; ECOG = Eastern Cooperative Oncology Group; EOT = end of treatment; GGT = gamma glutamyltransferase; HBsAg = hepatitis B surface antigen; HIV = human immunodeficiency virus; INR = international normalised ratio; LDH = lactate dehydrogenase; MRI = magnetic resonance imaging; NCI CTCAE = National Cancer Institute Common Terminology Criteria for Adverse Events; PET = positron emission tomography; PT = prothrombin time; PK = pharmacokinetics; RBC = red blood cell; WBC = white blood cell; ULN = upper limit of normal.											
[a] Except Cycle 1 Day 1, if visit is missed theoretical cycles dates (7 days ± 3) are kept constant irrespectively of whether the visit is done and/or the study treatment is administered or not. If a participant does not attend for CnD1 visit, the CnD1 assessments will still need to be performed (and shall be recorded on the unscheduled visit in the eCRF).											

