[b] Following the 30-day safety follow up, when clinically appropriate, it is also recommended the participant be monitored with dermatologic examinations and chest CT scans for cutaneous and non-cutaneous secondary malignancies for up to 6 months after the last study treatment dose or until initiation of another antineoplastic therapy											
[c] Cycle 1 Day1 refers to the day the participant receives the first dose of study treatment. Day 1 of Cycle 2 and of each subsequent cycle corresponds to Day 29 of the previous cycle.											
[d] Physical examination: At baseline: physical examination includes general appearance, neck (including thyroid), eyes, ears, nose, throat, lungs, heart, abdomen, back, lymph nodes, extremities, vascular and neurological. If indicated based on medical history and/or symptoms, rectal, external genitalia, skin, breast and pelvic examinations should be performed. Ophthalmic examination, at baseline, should include visual acuity (Snellen chart or equivalent, see Appendix 5), tonometry (intraocular pressure), slit lamp examination, and fundoscopy. Ophthalmic examination should be repeated at subsequent visits if clinically indicated. During treatment phase, at EOT visit and at Safety 30 day follow-up visit physical examination should be targeted as clinically indicated.											
[e] Vital signs include blood pressure, pulse rate, body temperature and respiratory rate											
[f] Dermatological examinations are to be performed every 8 weeks from Cycle 1 Day 1 (i.e. on Day 1 of Cycles 3, 5, 7, etc...) until the end of treatment. Following the 30-day follow-up, when clinically appropriate, it is recommended participants be monitored with dermatologic for up to 6 months after the last study treatment dose to check for possible keratoacanthoma and/or squamous cell carcinoma											
[g] Hematology: hemoglobin, hematocrit, RBC, WBC with differential (absolutes values), platelet counts, neutrophils, lymphocytes, monocytes, basophils, eosinophils											
[h] Procedure does not have to be repeated if performed within 72 hours prior to Cycle 1 Day 1 (i.e. first day of dosing)											

Cycle / Visit	Screening	Cycle 1				Cycle 2		Subsequent Cycles[a]			EOT visit	Safety 30-day follow-up visit[b]
		Odd cycles		Even cycles								
	Day -28 to -1	D1[c] Inclusion/ Baseline	D8	D15	D22	D1 ± 3 days	D28 ± 7 days	D1 ± 3 days	D1 ± 3 days	D28 ± 7 days	± 3 days	+ 7 days after EOT visit/last dose if EOT not performed

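### As worded, the baseline rule shuts out a Cycle 1 Day 1 value with a recorded predose time but accepts the same value without a time

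*SAP*

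**What the plan says.** SAP 5.1 gives the general rule: "Baseline is defined as the last completed and available assessment prior to date of first dose of study treatment (including unscheduled or re-test"). Its next sentence covers one same-day case. An assessment that the protocol plans before the first dose, and that "is performed on the same day as the first dose of treatment and the time is unknown", is presumed predose and taken as baseline. Nothing is said about a same-day assessment whose predose time is known. Protocol 9.4.1 has the same two sentences, apart from the mention of unscheduled values: "Baseline is defined as the last completed and available assessment prior to date of first dose of study treatment".

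The schedule of activities (protocol Table 1, SAP Table 3) heads the first-dose visit "D1[c] Inclusion/ Baseline". Its footnote c says: "Cycle 1 Day1 refers to the day the participant receives the first dose of study treatment". Vital signs and ECOG status are required at that visit with no waiver. Physical examination with weight, hematology, chemistry, coagulation, urinalysis and the pregnancy test are required unless done in the preceding 72 hours. Before that, SAP 1.2.1 says that participants "will be screened for eligibility in the 28 days before the first dose of encorafenib".

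ECG has its own rule in SAP 5.1. Its baseline comes from measurements taken before the first administration, not before the date of that administration.

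**The concern.** A baseline should be the last value before exposure. Tying it to a calendar date excludes the whole first-dose day, including measurements taken before the capsules were swallowed. The only way back in is to have no recorded time, so the better-documented value is the one rejected.

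The protocol plans these Day 1 measurements as predose. For vital signs, section 8.3.6 says: "All assessments during the treatment phase should be made prior to study treatment administration and before blood collection for laboratory tests". Inclusion criteria 9 to 11 also require adequate laboratory function both at screening and at baseline, so the protocol treats these as two occasions.

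Changes in laboratory parameters and vital signs are named secondary endpoints. A programmer who follows the text literally would measure them from an older value than the one the schedule collects for this purpose.

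**Working it through.** The plan states no figure to reproduce. The check applies the written rule to each kind of assessment and then asks which value takes its place.

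**Step 1. Classify the assessments.** Condition A is that the assessment falls before the date of first dose. Condition B is that it falls on that date, was planned predose and has an unknown time.

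| Assessment | A | B | Eligible as written |
|---|---|---|---|
| Before Day 1 | yes | no | yes |
| Day 1, planned predose, no time recorded | no | yes | yes |
| Day 1, predose time recorded | no | no | no |
| Day 1, postdose time recorded | no | no | no |

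Row 3 is the defect. Rows 2 and 3 can be the same measurement, differing only in whether a time was entered.

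**Step 2. Age of the substitute value.** Inputs are the screening window (Day -28 to Day -1) and the 72-hour waiver (footnote h of the schedule).

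- Vital signs and ECOG status (no waiver): 1 to 28 days, against 0 days for the Day 1 value.
- Waivable items that had to be repeated on Day 1: the earlier value is by construction more than 72 h / 24 h = 3 days old, and up to 28 days.
- Waivable items done within 72 hours and not repeated: at most 3 days old. The rule causes no loss here.
- Unscheduled or re-test values before Day 1 shorten these ages. Laboratory samples may also be drawn up to 48 hours before a visit (protocol 8.3.4, SAP 5.6.3), in which case they are already dated before Day 1.

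**Step 3. Outputs that use this baseline.** These are changes from baseline and CTCAE or normal/abnormal shift tables for laboratory tests, and laboratory notable shifts (SAP 5.6.3.1 to 5.6.3.3). They also include changes from baseline, blood-pressure shift tables and baseline-relative notable criteria for vital signs and weight (SAP 5.6.4, 5.6.5), and the ECOG shift table (SAP 5.6.8). The body-temperature criteria are absolute and do not depend on it.

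**Step 4. Illustration with invented readings.** Take systolic pressure of 138 mmHg at screening, 162 predose on Day 1 and 161 on Day 15. SAP 5.6.5 calls a value notable if it is at least 160 and has risen by at least 20 mmHg.

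- Baseline 138: 161 - 138 = +23. Notable; shift from Grade 1 to Grade 3.
- Baseline 162: 161 - 162 = -1. Not notable; Grade 3 at both times.

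One participant is 1/3 = 33% of a table of three and 1/6 = 17% of a table of six. The example shows how the flag can flip, not how often.

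**Step 5. Outputs that do not use it.** DLTs are taken from the flag on the adverse event form (SAP 5.3.1). The tolerability decision rests on the DLT rate, deaths, serious events and events leading to discontinuation or dose change (SAP 5.8.1). No Day 1 ECG is scheduled, and SAP 5.1 identifies the screening ECG as baseline.

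**The case against.** The strongest reply is that the intent is clear. The same-day sentence presumes an untimed assessment was predose and for that reason accepts it, which makes sense only if predose Day 1 values count. The ECG wording points the same way. This stands as a reading of intent. It does not cure the text, because the first sentence still excludes the day and the second readmits only unknown times.

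A reader might infer several stronger things that the documents do not support:

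- *Every participant loses the Day 1 baseline, or sites will differ.* Exact clock times are specified for PK samples, but no section says the forms for vital signs, weight, ECOG status or laboratory tests capture a time. If they do not, the exception makes planned predose Day 1 values baseline for everyone and nobody is affected. A site difference is conjecture, since all sites use one eCRF.
- *Baseline will be 28 days old.* That is a ceiling, as step 2 shows.
- *A predose Day 1 abnormality will be reported as arising on treatment.* SAP 5.1 limits worst post-baseline analyses to on-treatment values, and the schedule places Day 1 in the screening epoch. On-treatment is not defined, so some ambiguity remains, but the text largely answers the point.
- *The ECG rule and the general rule give conflicting results.* The wording differs, but with no Day 1 ECG scheduled the difference has no effect.

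It is also fair that nothing is formally tested, and that individual laboratory and vital-sign values are listed, so a Day 1 reading stays visible.

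**Conclusion.** The point holds as a wording defect with a real but limited effect. Read literally, both documents replace a timed predose Day 1 value with an earlier one, against the schedule's own label for that visit and the evident purpose of the same-day sentence. Where this happens, the baseline is 1 to 28 days old for vital signs and ECOG status. It is more than 3 and up to 28 days old for waivable items repeated on Day 1, unless an unscheduled or re-test value lies in between.

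The effect is confined to descriptive safety outputs that are relative to baseline. It depends on two things the documents do not settle: whether the forms record a time, and whether programming follows the letter or the intent. The number of participants affected therefore cannot be computed. ECG baseline, the primary endpoint and the below-33% rule do not change. The wording should still be corrected, because it is a stated rule that yields a worse baseline for named secondary endpoints and the correction is simple.

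**What to change.** In SAP 5.1, replace the anchor on the date of first dose with one on the dose itself, for example: the last completed and available assessment before the first administration of study treatment (date and time). The ECG rule in the same section already uses that anchor. Keep the rule that a planned predose same-day assessment with unknown time counts as predose. Make the same change in protocol 9.4.1 at the next opportunity so that the two documents agree.

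A sentence stating that predose Day 1 values are not post-baseline values is optional, given the on-treatment restriction, but would settle what that term means.

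The cost is one phrase in each document. No data collection or procedure changes.

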Abbreviations: AE = adverse event; ALT = alanine aminotransferase; aPTT = activated partial thromboplastin time; AST = aspartate aminotransferase; β-HCG = beta human chorionic gonadotropin; BUN = blood urea nitrogen; CK = creatine kinase; CT = computed tomography; eCRF = electronic case report form; D=Day; ECG = electrocardiogram; ECOG = Eastern Cooperative Oncology Group; EOT = end of treatment; GGT = gamma glutamyltransferase; HBsAg = hepatitis B surface antigen; HIV = human immunodeficiency virus; INR = international normalised ratio; LDH = lactate dehydrogenase; MRI = magnetic resonance imaging; NCI CTCAE = National Cancer Institute Common Terminology Criteria for Adverse Events; PET = positron emission tomography; PT = prothrombin time; PK = pharmacokinetics; RBC = red blood cell; WBC = white blood cell; ULN = upper limit of normal												
[a] Except Cycle 1 Day 1, if visit is missed theoretical cycles dates (7 days ± 3) are kept constant irrespectively of whether the visit is done and/or the study treatment is administered or not. If a participant does not attend for CnD1 visit, the CnD1 assessments will still need to be performed (and shall be recorded on the unscheduled visit in the eCRF)												
[b] Following the 30-day safety follow up, when clinically appropriate, it is also recommended the participant be monitored with dermatologic examinations and chest CT scans for cutaneous and non-cutaneous secondary malignancies for up to 6 months after the last study treatment dose or until initiation of another antineoplastic therapy												
[c] Cycle 1 Day 1 refers to the day the participant receives the first dose of study treatment Day 1 of Cycle 2 and of each subsequent cycle corresponds to Day 29 of the previous cycle												

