5.6.3.1. Hematology and Clinical Chemistry

Descriptive statistics of all parameters over time will be performed. Values at each visit and changes from baseline will be calculated and tabulated. Unscheduled visits or retest will not be analyzed.

Shift tables of maximum post baseline NCI CTCAE grades according to baseline NCI CTCAE grade (version 4.03) will be provided for the following parameters:

- Hematology
 - o Hemoglobin (Low)
 - o Hemoglobin (High)
 - o Leukocytes (Low)
 - o Leukocytes (High)
 - o Neutrophils (Low)
 - o Platelets (Low)

Sponsor Name: Pierre Fabre Médicament

Sponsor Protocol ID: W00090GE102

PII

- Lymphocytes (Low)
- Lymphocyte (High)

- Biochemistry

- Phosphate (Low)
- Alanine Aminotransferase (High)
- Albumin (Low)
- Alkaline Phosphatase (High)
- Amylase (High)
- Aspartate Aminotransferase (High)
- Bilirubin (High)
- Calcium Corrected (Low)
- Calcium Corrected (High)
- Creatine Kinase (High)
- Creatinine (High)
- Gamma Glutamyl Transferase (High)
- Glucose (Low)
- Glucose (High)
- Lipase (High)
- Magnesium (Low)
- Magnesium (High)
- Potassium (Low)
- Potassium (High)
- Sodium (Low)
- Sodium (High)
- Urate (High) corresponding to uric acid

Laboratory data will be graded using NCI CTCAE Version 4.03. Grade 0 will be assigned for all non-missing values not graded as ≥ 1 . Grade 5 will not be used.

Scatter plots of maximum post-baseline NCI CTCAE grade according to baseline grade will also be produced.

For some parameters, grades are defined for low and high values.

In addition, incidence of clinically notable shifts in laboratory parameters based on NCI CTCAE grade for the same list of parameters (as above) will be summarized, i.e. number and percentage

Sponsor Name: Pierre Fabre Médicament

Sponsor Protocol ID: W00090GE102

PII

of participants with at least one clinically notable shift during study. Clinically notable shift is defined as a worsening from baseline by at least 2 grades, or to grade 3 or above.

For parameters that cannot be graded with NCI CTCAE, shift tables of worst post baseline normal/abnormal level according to baseline normal/abnormal level will be displayed.

Hepatic toxicity

Possible Hy's Law cases will be summarized as part of the analysis below (last category of Table 5).

Hepatic toxicity will be assessed based on the following Liver Function Tests (LFTs): Albumin, ALT, AST, ALP and Total Bilirubin (TBL). For these parameters, NCI CTCAE grades are defined.

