5.6.5. Vital Signs

Tympanic temperature (°C), pulse rate (collected as heart rate in the vital signs eCRF, in beats/min), respiratory rate (breaths/min), Systolic Blood Pressure (SBP, in mmHg) and Diastolic Blood Pressure (DBP, in mmHg) will be measured using study site standard techniques at screening and repeated on Cycle 1 Days 1, 8, 15 and 22, Day 1 of each subsequent cycle, the end of treatment visit and the 30-day safety follow-up visit.

All parameters will be described at each scheduled visit with changes from baseline in participants from the SAF.

Sponsor Name: Pierre Fabre Médicament

Sponsor Protocol ID: W00090GE102

PII

In addition, shift tables of worst post baseline grade according to the baseline grade will be provided for blood pressure hypertension criteria (systolic, diastolic, and both combined). It will be derived as follows:

- Systolic BP (SBP) only (mmHg):
 - Grade 0: < 120
 - Grade 1: 120-139
 - Grade 2: 140-159
 - Grade 3: ≥ 160
 - No Grade 4 or 5
- Diastolic BP (DBP) only (mmHg):
 - Grade 0: < 80
 - Grade 1: 80-89
 - Grade 2: 90-99
 - Grade 3: ≥ 100
- Systolic and diastolic BP combined (mmHg). Maximum grade based on SBP and DBP values at the same assessment will be considered:
 - Grade 0: SBP < 120 and DBP < 80
 - Grade 1: SBP in 120-139 or DBP in 80-89
 - Grade 2: SBP in 140-159 or DBP in 90-99
 - Grade 3: SBP ≥ 160 or DBP ≥ 100
 - No Grade 4 or 5

The following criteria define clinically notable abnormalities:

- Clinically notable elevated values
 - Systolic blood pressure (BP): ≥ 160 mmHg and an increase ≥ 20 mmHg from baseline;
 - Diastolic BP: ≥ 100 mmHg and an increase ≥ 15 mmHg from baseline;
 - Pulse rate (collected as heart rate in the vital signs eCRF): ≥ 120 bpm with increase from baseline of ≥ 15 bpm;
 - Weight: increase from baseline of $\geq 10\%$;
 - Body temperature [C]: ≥ 37.5 C.

Sponsor Name: Pierre Fabre Médicament

Sponsor Protocol ID: W00090GE102

PII

- Clinically notable low values

- Systolic BP: ≤ 90 mmHg with decrease from baseline of ≥ 20 mmHg;
- Diastolic BP: ≤ 50 mmHg with decrease from baseline of ≥ 15 mmHg;
- Pulse rate (collected as heart rate in the vital signs eCRF): ≤ 50 bpm with decrease from baseline of ≥ 15 bpm;
- Weight: $\geq 20\%$ decrease from baseline;
- Body temperature [C]: ≤ 36 C.

Number and percentage of participants with at least one of each post-baseline vital sign clinically notable abnormality will be summarized by abnormality.

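### Required Day 1 assessments made up after a missed visit go on the unscheduled eCRF page, and the SAP then leaves them out of the by-visit safety summaries

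*SAP*

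**What the plan says.** **Recording rule.** Protocol Table 1, footnote [a], opens "Except Cycle 1 Day 1, if visit is missed theoretical cycles dates" and holds the theoretical cycle dates constant after a missed visit. For a participant who does not attend, it says "the CnD1 assessments will still need to be performed (and shall be recorded on the unscheduled visit in the eCRF". SAP Table 3 repeats the rule: "If a participant does not attend for CnD1 visit, the CnD1 assessments will still need to be performed".

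**Analysis rule.** SAP 5.1 says "For summary statistics by visit, only scheduled visits will be summarized", then "Re-test and unscheduled assessments will not be taken into account for summaries of post-baseline visit", then "For TFLs, visits will be identified as collected in CRF".

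**Where the exclusion recurs.**
- Hematology and chemistry (SAP 5.6.3.1): "Unscheduled visits or retest will not be analyzed". The same sentence appears for coagulation (5.6.3.2) and dipstick urinalysis (5.6.3.3).
- Vital signs (5.6.5): "All parameters will be described at each scheduled visit with changes from baseline in participants from the SAF".
- Weight (5.6.4), ECG (5.6.6) and dermatology (5.6.7) are likewise described by scheduled visit.
- ECOG (5.6.8) is described by visit without the word scheduled, so the general rule in 5.1 governs it.

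**What is kept.** SAP 5.1 uses unscheduled values for baseline and for worst post-baseline analyses. Laboratory, vital sign, ECG, dermatology and ECOG data are also listed.

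**The concern.** The usual reason for leaving unscheduled records out of by-visit tables is that they are extra: repeat tests, or tests prompted by an event. Here the same page also holds assessments that the protocol requires. The eCRF label therefore does not separate the two kinds of record, and the SAP relies on that label alone.

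Changes in laboratory parameters, vital signs and ECGs are a stated secondary endpoint, and SAP 5.4 adds dermatological examinations and ECOG status. Values and changes from baseline by visit are a main planned summary for these. With three to six participants, losing one person changes a visit's mean, median and range noticeably.

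**Working it through.** The documents give no figure on this point to reproduce. The check is a side-by-side reading, followed by arithmetic for scale.

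**Step 1: follow one record through the rules.** A participant misses a Day 1 visit in a later cycle.
1. Footnote [a]: the assessments are done late and entered as unscheduled.
2. SAP 5.1, visit labels: the record keeps the unscheduled label.
3. SAP 5.1, by-visit rule: the record is excluded from that visit's summary.
4. Search for a rescue rule: the SAP has no analysis window or re-mapping rule that would return the record to its Day 1.

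The record is therefore absent from the by-visit table although it was required and collected.

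**Step 2: scope.** The footnote excepts Cycle 1 Day 1. Its text would reach Cycle 2 Day 1 onward, but in Table 1 the marker sits on the header for subsequent cycles, so a narrow reading starts at Cycle 3. ECG is due only on Day 1 of even cycles, and dermatology only on Day 1 of odd cycles from Cycle 3, so each is exposed at fewer visits.

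**Step 3: what else holds the late value.**

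| Data | Summary table that can still use it | Listing |
|---|---|---|
| Hematology, chemistry, coagulation | Worst-value shift tables | Yes |
| Blood pressure | Worst-grade shift, notable values | Yes |
| Pulse, temperature, weight | Notable values | Yes |
| QT, QTcF, heart rate | Notable values | Yes |
| ECOG | Worst-value shift | Yes |
| Dipstick urinalysis | None | Yes |
| Dermatology | None | Yes |
| Respiratory rate | None | Yes |

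**Step 4: size per case.** The share lost is 1/n. With three participants, 1/3 = 33.3%, leaving 2. With six, 1/6 = 16.7%, leaving 5. Both figures assume that everyone is still on treatment. With two remaining, the share would be 1/2 = 50%.

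**Step 5: how often.** The documents give no missed-visit rate. Let q be an assumed chance that a participant misses a given Day 1 and has it made up as unscheduled, independently of the others. The chance of losing at least one participant at that visit is 1 − (1 − q)^n. For example, with q = 5% and n = 3 it is 1 − 0.95³ = 14.3%.

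| Assumed q | n = 3 | n = 6 |
|---|---|---|
| 2% | 5.9% | 11.4% |
| 5% | 14.3% | 26.5% |
| 10% | 27.1% | 46.9% |
| 20% | 48.8% | 73.8% |

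These figures show scale only; q is not a figure from the plan.

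**The case against.** **No study decision turns on this.** The primary endpoint comes from the DLT flag on the adverse event form (SAP 5.3.1). The TSC judges tolerability on the DLT rate, deaths, serious events and events that change or stop treatment (SAP 5.8.1). That is correct, and it limits the point to presentation of a secondary endpoint.

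**The signal survives elsewhere.** Worst-value analyses and listings keep the late values, and reporting the number of observations makes a gap visible. This stands for most parameters, but not for the three with no worst-value table.

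**A scheduled-visit mean should hold on-schedule values.** This is a defensible choice in general, and the ±3-day window already absorbs ordinary lateness. It does not explain why the protocol requires the late assessment as a Day 1 assessment while the SAP treats it like an incidental re-test.

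**A stronger reading.** A reader might infer that absentees are sicker, so that dropping them makes the by-visit profile look better than it is. The documents do not support this. They name vacation, holidays and logistics as reasons for interruption (Protocol 6.6.1), and SAP 5.2 plans a table of visits missed because of COVID-19. A treatment hold does not move the visit either, because cycle dates stay constant whether or not drug is given. A late value could be better or worse than the on-time one. Nor are by-visit and worst-value tables in contradiction when they differ, since they measure different things.

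**Conclusion.** The point holds as a conflict between the recording rule and the analysis rule. Protocol-required Day 1 data made up after a missed visit (after Cycle 1 Day 1) are left out of by-visit values and changes from baseline. Each case costs one participant at that visit, 33.3% of three or 16.7% of six if all remain on treatment. How often this will occur cannot be derived from the documents, and the direction of any bias is unknown.

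It should be corrected, but it is a modest defect in a descriptive study. It does not touch the primary endpoint, the TSC decision, adverse event tables, worst-value analyses or listings. The clearest loss is for dipstick urinalysis, dermatology and respiratory rate, where the late result would be in no summary table. The conclusion assumes that sites follow footnote [a] and that programming follows SAP 5.1 as written.

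**What to change.** Add to SAP 5.1 a rule on these lines: assessments identified as replacing a missed Day 1 visit after Cycle 1 are assigned to that Day 1 and included in by-visit summaries. To qualify, a record must:
- fall between the start of the Day 1 window (theoretical date − 3 days) and the next scheduled visit;
- be the first such record for the parameter;
- not be a re-test or a test prompted by an adverse event.

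Listings show the actual study day. All other unscheduled and re-test values stay excluded.

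Two existing rules must be amended to except these records, or they will contradict the new one: the visit-label rule in 5.1, and the exclusion sentence in 5.6.3.1, 5.6.3.2 and 5.6.3.3. The SAP should also say how a replacement record is identified, for example by an eCRF entry or a data-review decision documented before database lock.

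The cost is a small visit-mapping derivation and these edits. The downside is that some mapped values will lie off the nominal day, in the extreme just before the next visit, which is why the actual day needs to be shown.
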